## 12.7 Medication and Adverse Event Coding Dictionaries

- Concomitant medications are coded using the March 2018 version of the World Health Organization Drug Coding Dictionary (WHODD).
- Adverse events are coded using version 21.0 of the Medical Dictionary for Regulatory Activities (MedDRA).

## 12.8 Protocol Deviations and Violations

Subject data will be examined for evidence of protocol deviations and violations in order to assess how well the investigators followed the protocol. A protocol deviation is a variation from processes or procedures defined in a protocol. Deviations usually do not preclude the overall evaluability of subject data and are often acknowledged and accepted in advance by the Sponsor. A protocol violation is a significant departure from processes or procedures that were required by a protocol. Violations often result in data that are not deemed evaluable for PK or efficacy analysis and may require that the subject(s) who violate the protocol be discontinued from the study.

A sponsor designee will perform a final review of the list of protocol deviations and violations prior to database lock and according to data available on the eCRF to adjudicate the categorization of the protocol deviations and violations.

# 13 STATISTICAL ANALYSIS

## 13.1 Baseline Parameters, Demographics, Medical History, Hyperhidrosis History, Concomitant Medications, Disposition and Drug/Alcohol Screening, and Pregnancy Testing

- The total number of subjects enrolled in the study.
- Subject demographics and baseline characteristics will include, date of birth, gender, race, ethnicity, height and weight, and age at onset and duration of hyperhidrosis, will be summarized and listed. Descriptive statistics (mean, SD, median, minimum, and maximum for numerical variables; count and percentage for categorical variables) will be presented where applicable.

- Subject medical, hyperhidrosis and medication history will be listed by MedDRA system organ class and preferred term (PT). A listing sorted by subject number, MedDRA system organ class and PT, and onset date will also be presented.
- Subject medication history will be mapped according to the WHODD.
- A listing of subject disposition will include start date and time of first study drug application in the extension study.
- The number of subjects who complete treatment (Day 168 [ $\pm 5$  days], EOT) will be summarized and listed.
- The number of subjects who complete study (Day 182 [ $\pm 5$  days], EOS) will be summarized and listed.
- The number of subjects who prematurely discontinue from the study and reason for discontinuation will be summarized and listed. The number of subjects who prematurely withdraw from study drug but remaining in the study will be summarized.
- Concomitant medications (start date on or after Day 1 of Study BBI-4000-CL-105) will be summarized using descriptive statistics.
- Use of concomitant medications (chronic medications or as needed medications e.g., acetaminophen, EMLA cream) are permitted during the screening and active study period (Day 1 through Day 168 [ $\pm 5$  days]) and will be recorded on the eCRF.
- Changes in concomitant medication usage will be recorded on the eCRF. If the reason for change is related to an AE, the event will be recorded in as an AE in the eCRF.
- Concomitant medications will be mapped according to the WHODD and will be presented in data listings.
- Drug and alcohol screen by visit will be listed.
- Pregnancy test (positive or negative) by visit will be listed.

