6.3.3 Medication History

Medications taken within the last month (30 days) prior to first dose of sofrironium bromide gel, 15% under Study BBI-4000-CL-105 and within 1 week prior to Screening/Enrollment (Week 0 [Day 1]) will be recorded in the source document and on the eCRF. Also refer to [Section 6.13](#) concomitant medications and restrictions for additional information.

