6.13 Concomitant Medications

6.13.1 General

Use of chronic medications or as-needed medications (e.g., acetaminophen, topical anesthetic [EMLA]) will be permitted during the screening and active study period (unless otherwise

restricted, refer to [Section 6.13.2](#)), and should be recorded in the source document and on the eCRF. Any changes in concomitant medication usage will be recorded in the source documents and on the eCRF. If the reason for change is related to an AE, the event should be recorded in the source documents and as an AE in the eCRF.

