6.13.2 Concomitant Medication Restrictions

The following medications will not be permitted during the study period:

- Botulinum toxin to the axillary area
- Newly prescribed anti-anxiety, anti-depressant, and/or psychostimulants (e.g., amphetamine) or drugs with known anticholinergic side effects
- Any cholinergic drug (e.g., bethanechol)
- Newly prescribed serotonergic agonist (or drugs that increase serotonin activity including SSRIs), betablocker, alpha-adrenergic agonist (clonidine), dopamine partial agonist or tricyclic antidepressant treatment
- Anticholinergic agents used to treat conditions such as, but not limited to, hyperhidrosis, asthma, incontinence, gastrointestinal cramps, and muscular spasms by any route of administration (e.g., intravenous, oral, inhaled, topical, etc.)
- Any topical prescription treatment for hyperhidrosis
- Any oral or topical homeopathic or herbal treatment (i.e., alternative therapies such as sage tablets, chamomile, valerian root and St. John's Wort)
- Use of potent inhibitors of cytochrome P450 CYP3A (including grapefruit juice) & CYP2D6 and transporter inhibitor (OCT2/MATE1/MATE2). Use of topical antifungal medications is permitted if not applied in the treatment area.

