## 12.6 Missing Safety and Efficacy Data

Adverse events recorded with ambiguous or missing start dates and times will be assumed to have started after the first dose of study drug on Day 1 of Study BBI-4000-CL-105. Consequently, such AEs will be included in all summaries of treatment-emergent adverse events (TEAE). Start and end dates and times for AEs will be listed as collected.

Where the start or end date of a concomitant medication is ambiguous or missing, the medication will be assumed to have been started before and continued after the first dose of study drug in Study BBI-4000-CL-105. That is, the medication will be listed as both prior and concomitant and included in the summary table of concomitant medications.

All other cases of missing or invalid data will be treated as missing and will not be imputed. Start and end dates for concomitant medications will be listed as collected.

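### SAP 13.1 leaves a medication with a known start before CL-105 Day 1 that continues during treatment out of the concomitant summary, while SAP 12.6 includes the same profile when a date is missing

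*SAP*

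**What the plan says.** The rule is in SAP 13.1: "Concomitant medications (start date on or after Day 1 of Study BBI-4000-CL-105) will be summarized using descriptive statistics". Neither that bullet nor the rest of the section covers a medication that began earlier and is still being taken. The next bullet nevertheless counts long-term treatment as concomitant: "Use of concomitant medications (chronic medications or as needed medications e.g., acetaminophen, EMLA cream) are permitted during the screening and active study period".

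SAP 12.6 deals with incomplete dates. Its trigger is "Where the start or end date of a concomitant medication is ambiguous or missing". In that case "the medication will be assumed to have been started before and continued after the first dose of study drug in Study BBI-4000-CL-105", and the consequence is that "the medication will be listed as both prior and concomitant and included in the summary table of concomitant medications".

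On the protocol side, section 6.13.1 allows "Use of chronic medications or as-needed medications" unless section 6.13.2 restricts them. Some of those restrictions apply only to new prescriptions, for example "Newly prescribed anti-anxiety, anti-depressant, and/or psychostimulants". Section 6.3.3 already collects earlier use: "Medications taken within the last month (30 days) prior to first dose" of study drug in CL-105 are recorded. Section 11.3.2 plans descriptive summaries of both prior and concomitant medications.

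The SAP's preliminary output list (Appendix A) has one medication summary, Table 14.1.4, for concomitant medications. It has one medication listing, 16.2.4.3, covering prior and concomitant medications. No prior-medication table is planned, and SAP 13.1 only lists medication history.

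**The concern.** A concomitant-medication table should show what subjects were taking while exposed to study drug. A rule based on start date shows what they began taking after a given day, which is a different set. Long-term treatment is the part of background medication most likely to fall between the two.

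The SAP also gives opposite answers for one exposure pattern. A medication begun before the first CL-105 dose and continued after it is summarized if a date is unknown and left out if the dates are known. Better data lead to exclusion. Two programmers working from this SAP could produce different versions of Table 14.1.4 and each cite a section in support.

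What is at stake is whether the background-medication summary in a small paediatric safety study is complete and reproducible. Readers of the ECG, vital-sign and adverse-event tables would reasonably look to that summary for long-term treatment and might take its absence to mean that there was none.

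**Working it through.** No figure in the plan needs reproducing. The check applies the wording of SAP 13.1 and 12.6 to each date pattern a medication record can have. Day 1 and first dose refer to CL-105.

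| Pattern | SAP 13.1 | SAP 12.6 | In Table 14.1.4? |
|---|---|---|---|
| 1. Start on or after Day 1, dates complete | In | Not triggered | Yes |
| 2. Start before Day 1, stopped before first dose, dates complete | Out | Not triggered | No, correctly: prior only |
| 3. Start before Day 1, stopped after first dose, dates complete | Out | Not triggered | No, although used during treatment |
| 4. Start missing or ambiguous | Cannot be applied | In, as prior and concomitant | Yes |
| 5. Start before Day 1, end blank because ongoing | Out | In, if a blank end date counts as missing | Undetermined |

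Patterns 3 and 4 show the contradiction. The profile that 12.6 assumes for pattern 4 is the profile actually recorded in pattern 3, yet the two are classified differently.

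Pattern 5 cannot be settled from the text. The 12.6 trigger covers a missing end date as well as a missing start date, which points to inclusion. But 12.6 speaks of a concomitant medication, and by the 13.1 start-date rule this record is not one, which points to exclusion. The SAP does not say whether an ongoing medication has a missing end date.

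**Are such records to be expected?** Two protocol provisions make them foreseeable.

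- Hormonal contraception counts as acceptable only if started at least 2 months before screening (Protocol 5.1 and 6.14.1). CL-108 screening coincides with CL-105 Day 8 (Protocol 4.1), which is 7 days after Day 1. Taking a month as 30 days, the latest compliant start is 60 − 7 = 53 days before CL-105 Day 1 (52 to 54 with the ±1 day allowance). If recorded as a medication with a known start date, it fails the 13.1 test for every compliant user.
- Protocol 6.13.2 bars several classes only when newly prescribed, among them psychostimulants, antidepressants, beta-blockers and clonidine. On that wording an established user may take part in CL-108. For these classes the 13.1 rule would show new starters, who breach the restriction, and omit fully dated long-term users, who do not.

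**Summary promised against summary planned.** Protocol 11.3.2 covers prior and concomitant medications. SAP Appendix A provides Table 14.1.4 only. A pattern 3 record therefore appears in no summary table.

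**Scale.** Maximum enrolment is 24 (SAP 11). One subject omitted from a drug row changes that row by 1/24 = 0.0417, or 4.2 percentage points; with fewer subjects the step is larger. The number of subjects affected cannot be derived from the documents.

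**The case against.** The strongest reply is that nothing is lost from reporting. Listing 16.2.4.3 covers prior and concomitant medications, SAP 12.3.1 says the listings report all data collected, and with at most 24 subjects a reader can check any individual's medications there. SAP 13.3.1 itself sends concomitant medications to listings, and the data that SAP 12.3.2 imports to support the PK analysis do not include medications. All of this stands. A reader might infer that these drugs vanish from the study report, or that Table 14.1.4 drives the safety and PK conclusions; the documents support neither. Nor does the point bear much on plasma levels through interacting drugs, since Protocol 6.13.2 prohibits potent CYP3A, CYP2D6 and OCT2/MATE inhibitors. Permitted established treatments remain.

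A second reply is that the SAP plainly regards long-term treatment as concomitant: 12.6 says so for the started-before-and-continued profile, and 13.1 names chronic medications. That also stands as evidence of intent. A reader might infer from the start-date rule that every ongoing medication with a known earlier start is dropped. That is not established, because a blank end date may bring it back under 12.6. Only records with complete dates are certain to be excluded. But evident intent does not repair the operative rule, which a programmer would implement as written.

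**Conclusion.** The point holds as an inconsistency between SAP 13.1 and 12.6, with a narrow but definite consequence: a fully dated medication begun before CL-105 Day 1 and continued during treatment is left out of Table 14.1.4, while the same profile with a missing or ambiguous date is included. For an ongoing medication with a blank end date the outcome is undetermined. The SAP also falls short of Protocol 11.3.2, because the omitted medications reach no summary table.

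The size is 4.2 percentage points per affected subject in a drug row at 24 subjects, with the number affected unknown. The expectation that some records will be affected rests on two assumptions: that contraceptives and established prescriptions are recorded as medications with known start dates, and that CL-105, whose own medication rules are not in these documents, did not exclude those users. No endpoint, test or analysis population changes. The correction is worth making before database lock because the stated rule gives an incomplete table and the remedy is small.

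**What to change.** In SAP 13.1, replace the start-date rule with definitions based on use, anchored to the first dose of study drug in CL-105:

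- Concomitant: any medication taken on or after that dose, whatever its start date.
- Both prior and concomitant: started before that dose and either ongoing or stopped on or after it.
- Prior only: stopped before that dose.

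Apply 12.6 to these definitions and the same anchor, and state that a medication recorded as ongoing does not have a missing end date. Keep the CL-105 anchor. A reader might prefer the first CL-108 application, but SAP 12.4, 12.6 and 13.1 all refer to CL-105, and moving the anchor for medications alone would turn a medication used only during the CL-105 week into a prior one and create a new mismatch.

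Add the prior-medication summary promised in Protocol 11.3.2, or record its omission as a change from the protocol.

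The cost is a few sentences in 12.6 and 13.1, routine reprogramming of one table and, if the summary is added, one further table. Protocol 6.3.3 and 6.13.1 already provide for recording these medications, and SAP 12.6 for listing their dates, so no new data are needed.

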### **13.2 Drug Exposure and Treatment Compliance**

- Study drug applications made or missed, and location (right and left axilla) will be recorded on the dosing diary card and data will be entered in the eCRF. Study drug applications and application location by day and by visit will be summarized.
- Study drug compliance will be evaluated at each visit during the treatment period. The site personnel will review the dosing diary card and weigh the pump container, with cap on, at Week 4 (Day 28 [ $\pm 3$  days]), Week 8 (Day 56 [ $\pm 5$  days]), Week 12 (Day 84 [ $\pm 5$  days]), Week 16 (Day 112 [ $\pm 5$  days]), Week 20 (Day 140 [ $\pm 5$  days]), and Week 24 (Day 168 [ $\pm 5$  days]). Amount (by weight) of study drug used by visit and overall difference in weight between Day 1 and final dose application on Day 168 [ $\pm 5$  days], will be summarized.

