4 STUDY DESIGN

4.1 General Description

This multi-center, open-label extension study will evaluate the long-term safety, tolerability, and pharmacokinetics of sofrironium bromide gel, 15%, when applied QD for up to 6 months in pediatric subjects \geq 9 years to \leq 17 years of age with axillary hyperhidrosis previously enrolled in Study BBI-4000-CL-105.

Following completion of the initial PK and safety study (Study BBI-4000-CL-105), subjects will be provided the opportunity to enter this 6-month open-label extension study. Subjects will be screened for eligibility at Day 8 of Study BBI-4000-CL-105 (last PK sample collection under BBI-4000-CL-105 study). Therefore, for participating subjects, the final treatment visit (i.e., Day 8/Visit 4) of Study BBI-4000-CL-105 and the Screening/Enrollment visit (i.e., Week 0 [Day 1]) of Study BBI-4000-CL-108 (long-term extension study) will take place simultaneously.

[figure not shown]
Subjects (parent/guardian) will be dispensed one container of sofrironium bromide gel, 15% each month at Visits 1-6. Subjects (and parent/guardian) will be instructed on the correct application procedure for sofrironium bromide gel, 15% (to be applied QD before bedtime to both axilla for up to 24 weeks).

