7.1 Screening/Enrollment (Week 0 [Day 1])

The final visit (Day 8/Visit 4) of Study BBI-4000-CL-105 and Screening/Enrollment (Week 0 [Day 1]) of this long-term extension Study BBI-4000-CL-108 will take place simultaneously. Therefore, procedures required under Study BBI-4000-CL-105, which are also required under the extension study will be recorded. The length of the additional time to complete additional activities associated with Screening/Enrollment visit is approximately 1.5 hours.

- Informed Consent Process
 - The parent(s)/legal guardian (s) must provide written informed consent prior to any study procedure being done; and
 - If able, the subject must provide assent to participate in the study.
- Interview
 - Evaluate Inclusion/Exclusion criteria\
- Assessments
 - Obtain and record vital signs
 - Record local tolerability assessment
- Sample Collection
 - Collect blood samples for safety laboratory testing (hematology and chemistry), and pregnancy testing (as applicable)
 - Collect urine sample for urine laboratory testing, routine urinalysis and pregnancy testing (females only)
- Instructions
 - Inform parent/guardian (caregiver) and subject that dosing will occur in the evening at approximately the same time before bedtime.
 - One pump container of sofrironium bromide gel, 15%, enough for 1 month of dosing, and one dosing diary card will be dispensed.
 - Review instructions for study drug application and use of the dosing diary card.
 - Study site personnel will prime the sofrironium bromide gel, 15% pump container with five (5) sequential actuations.
 - Weigh the sofrironium bromide gel, 15% primed pump container with cap.

- Provide study product application instruction brochure to subject (parent/guardian).
- Provide gloves if study drug to be dispensed by a parent/guardian.
- The next visit will be scheduled.

7.2 Treatment: Week 4 (Day 28 [± 3 days]) through Week 24 (Day 168 [± 5 days])

Visits will occur at Week 4 (Day 28 [± 3 days]), Week 8 (Day 56 [± 5 days]), Week 12 (Day 84 [± 5 days]), Week 16 (Day 112 [± 5 days]) and Week 20 (Day 140 [± 5 days]). It is estimated that each visit will take approximately 1.5 hours.

- Interview
 - Update medications since last visit
 - Assessment of AEs
- Assessments
 - Obtain and record vital signs
 - Perform an abbreviated physical examination
 - Complete an ECG at Week 4 (Day 28 [± 3 days])
 - HDSM-Ax (or HDSM-Ax, Child) and PGI-S assessment (completed by the subject)

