 - Application site (axillae) tolerability assessment (completed by subject prior to Investigator assessment, and Investigator assessment)
- Review dosing diary card (compliance check) at each visit.
- Sample Collection
 - Collect blood sample for safety laboratory testing and PK and urine sample for urine laboratory testing at Week 4 (Day 28 [± 3 days]);
 - Collect urine sample for pregnancy testing (as applicable) at all visits
- Instructions
 - Collect subject's previously dispensed sofrironium bromide gel, 15%, pump container from prior visit. Record weight of container with cap.
 - Collect subject's completed dosing diary card from prior visit and review for compliance.
 - Prime and weigh to-be-dispensed sofrironium bromide gel, 15% pump container with cap prior to dispensing.
 - Dispense one sofrironium bromide gel, 15%, pump container and one dosing diary card.
 - Provide gloves if study drug to be dispensed by a guardian (caregiver).
 - Remind subject to return sofrironium bromide gel, 15% pump container and dosing diary card for the next study visit.
 - The next visit will be scheduled.

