7.3 End of Treatment/Early Termination: Week 24 (Day 168 [± 5 days])

It is estimated that each visit will take approximately 1.5 hours.

- Interview
 - Update medications since last visit
 - Assessment of AEs
- Assessments
 - Obtain and record vital signs
 - Perform an abbreviated physical examination
 - Complete an ECG
 - HDSM-Ax (or HDSM-Ax, Child) and PGI-S assessment (completed by the subject)
 - PGI-C assessed
 - Application site (axillae) tolerability assessment (completed by subject prior to Investigator assessment, and Investigator assessment)
- Review dosing diary card (compliance check)
- Sample Collection
 - Collect blood sample for safety laboratory testing and PK and urine sample for urine laboratory testing
 - Collect urine sample for pregnancy testing
- Instructions
 - Collect subject's previously dispensed sofrironium bromide gel, 15%, pump container from prior visit. Record weight of container with cap.
 - Collect subject's completed dosing diary card from prior visit and review for compliance.
 - The next visit will be scheduled.

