8.1.2 Packaging and Labeling

Study drug is packaged in a white colored, metered pump container. One pump container is packaged in a carton with 2 applicators. The total gel volume in each pump container is approximately 50 mL (~43 g). The gross weight of each full container at baseline is approximately 78 to 84 grams. One full pump actuation delivers ~0.67 mL of the gel formulation. Therefore, each pump container is sufficient for 30 days of dosing per protocol instructions. The external carton will be labeled with “Caution: New Drug – Limited by Federal Law to Investigational Use”.

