## 3 STUDY OUTLINE

This multicenter, open-label extension study will evaluate the long-term safety, tolerability, and PK of sofspironium bromide gel, 15%, when applied (QD) for up to 6 months in pediatric subjects  $\geq 9$  years to  $\leq 17$  years of age with axillary hyperhidrosis previously enrolled in Study BBI-4000-CL-105.

Following completion of the initial PK and safety study (Study BBI-4000-CL-105), subjects will be provided the opportunity to enter a 6-month open-label extension study. Subjects will be screened for eligibility at Day 8 of Study BBI-4000-CL-105 (last PK sample collection under BBI-4000-CL-105 study). Therefore, for participating subjects, the final treatment visit (i.e., Day 8/Visit 4) of Study BBI-4000-CL-105 and the Screening/Enrollment visit (i.e., Week 0 [Day 1]) of Study BBI-4000-CL-108 (long-term extension study) will take place simultaneously.

Subjects (parent/guardian) will be dispensed one container of sofspironium bromide gel, 15% each month at Visits 1-6. Subjects (and parent/guardian) will be instructed on the correct application procedure for sofspironium bromide gel, 15% (to be applied QD before bedtime to both axilla for up to 24 weeks).

[figure not shown]
Vital signs, review of concomitant medications, assessment of adverse events (AEs), completion of patient-reported outcomes (Hyperhidrosis Disease Severity Measure-Axillary [HDSM-Ax] and Hyperhidrosis Disease Severity Measure-Axillary, Child [HDSM-Ax, Child] and Patient Global Impression of Severity [PGI-S]), and urine pregnancy tests (UPT) for all females will be done each visit. Application site tolerability will be assessed at all visits through the end of treatment (EOT) at Week 24 (Day 168 [ $\pm 5$  days]). Blood and urine for safety testing will be collected and analyzed at Week 4 (Day 28 [ $\pm 3$  days]) and Week 24 (Day 168 [ $\pm 5$  days]) for routine hematology, chemistry, and urinalysis parameters. Electrocardiograms (ECGs) will be

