## 8 DOSING AND COMPLIANCE

All subjects will receive active study drug. One dose of sofrironium bromide gel, 15% will be applied topically using the supplied applicator to each axilla QD at approximately the same time before bedtime for up to 24 weeks. Sofpironium bromide gel is packaged in airless, multi-dose, metered pump containers. Each administration of sofrironium bromide gel, 15% is  $\sim$ 0.67 mL and contains 86.5 mg of sofrironium bromide, for a total daily dose when applied to both axillae of 173 mg.

The subject and/or the parent(s)/guardian(s) will record that the study drug was applied to each axilla (right and left) and when the subject applied the study drug in the dosing diary card. The site personnel will review the dosing diary card and weigh the pump container, with cap on, at Week 4 (Day 28 [ $\pm$ 3 days]), Week 8 (Day 56 [ $\pm$ 5 days]), Week 12 (Day 84 [ $\pm$ 5 days]), Week 16 (Day 112 [ $\pm$ 5 days]), Week 20 [Day 140 [ $\pm$ 5 days]), and Week 24 (Day 168 [ $\pm$ 5 days]).

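### SAP 13.2 takes overall drug use by weight from a Day 1 to Day 168 difference that spans two different containers; it should state a sum over all six

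*SAP*

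**What the plan says.** SAP 13.2 (Drug Exposure and Treatment Compliance) lists two weight summaries in one sentence: "Amount (by weight) of study drug used by visit and overall difference in weight between Day 1 and final dose application on Day 168", with a window of ±5 days on the last day. It gives no formula for either and lists only the weighings at Weeks 4 to 24.

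SAP 3 states that "Subjects (parent/guardian) will be dispensed one container of sofspironium bromide gel, 15% each month at Visits 1-6", and Protocol 4.1 says the same. The Protocol's visit sections set out the weighing:

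- **Day 1 (Protocol 7.1):** "Weigh the sofrironium bromide gel, 15% primed pump container with cap". This is container 1, after five priming actuations.
- **Weeks 4 to 20 (Protocol 7.2):** the used container is returned and weighed, and for the next one the instruction is "Prime and weigh to-be-dispensed sofrironium bromide gel, 15% pump container with cap prior to dispensing".
- **Week 24 (Protocol 7.3):** staff collect the "pump container from prior visit. Record weight of container with cap". The prior visit is Week 20, so this is container 6.

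Protocol 11.3.4 asks for the amount of study drug by weight and the number of days of application to be summarized. It does not ask specifically for an overall total.

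**The concern.** A Day 1 to Day 168 weight difference measures total use only if a single container is used throughout. With six containers, the literal subtraction sets container 1's dispensing weight against container 6's return weight. The result is container 6's use plus whatever difference there was between the two starting weights. Use from containers 1 to 5 does not enter.

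The literal measure would therefore be low, and it would also fail to rank subjects by exposure. With equal starting weights, a subject who applied nothing for 20 weeks and then dosed daily would score the same as a fully adherent subject. A subject who was adherent to Week 20 and returned container 6 unused would score zero.

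At stake is one descriptive line on exposure, in a study of safety over up to 24 weeks of use. If programmed literally, that line would also disagree with the by-visit amounts named in the same sentence.

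**Working it through.** **Inputs**

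- Gel per container: "The total gel volume in each pump container is approximately 50 mL (~43 g"), Protocol 8.1.2.
- Gel per actuation: about 0.67 mL; gross weight of a full container: about 78 to 84 g (both Protocol 8.1.2).
- Dose: 86.5 mg per axilla, "for a total daily dose when applied to both axillae of 173 mg" (SAP 8). This means two actuations a day.
- Priming: five actuations (Protocol 7.1), taken to be the same for every container.
- Visits: Day 140 ±5 and Day 168 ±5 for Visits 6 and 7 (SAP 12.5).
- Dosing is in the evening, and subjects are told not to apply drug before a visit (Protocol Appendix C).

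**The plan's own figures**

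- Daily dose: 2 × 86.5 = 173 mg, as stated.
- Container capacity after priming: (50 − 5 × 0.67) / (2 × 0.67) = 34.8 days, which covers the stated 30 days.

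**Gel used per day, by two routes**

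1. From packaging: 43/50 = 0.86 g/mL; 0.67 × 0.86 = 0.5762 g per actuation; × 2 = 1.152 g/day.
2. From dose, taking 15% as weight for weight: 173 mg / 0.15 = 1.153 g/day.

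The two routes agree.

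**Actual use by a fully adherent completer on nominal days**

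- Container 1 serves the evenings of Days 1 to 27 (27 doses), and containers 2 to 6 serve 28 each: 27 + 5 × 28 = 167 doses. Counting a Day 168 dose gives 168.
- 167 doses: 192.5 g (route 1) or 192.6 g (route 2).
- 168 doses: 193.6 g or 193.8 g.

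**The literal measure**

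Write S for a container's primed dispensing weight and R for its return weight. Then

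S1 − R6 = (S6 − R6) + (S1 − S6).

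The first term is use from container 6. The second has nothing to do with use.

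| Case | Calculation | Result |
|---|---|---|
| Nominal days, S1 = S6 | 28 × 1.152 | about 32 g |
| Nominal days, S1 and S6 up to 84 − 78 = 6 g apart | 32.3 ± 6 | about 26 to 38 g |
| S1 = S6, shortest last interval (28 − 10 = 18 days) | 18 × 1.152 | about 21 g |
| S1 = S6, longest last interval (28 + 10 = 38 days) | 38 × 1.152 = 43.8 g, capped by contents after priming: 43 − 5 × 0.5762 | about 40 g |

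Each range varies one source alone; together they would be wider. On nominal days the share captured is 28/167 = 16.8% or 28/168 = 16.7%, about one sixth.

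**The proposed sum**

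The sum of (S − R) over containers 1 to 6 returns the 192 to 194 g above, because each term compares a container with itself.

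**The case against.** The strongest reply is that the SAP names no container and writes no subtraction. The phrase stands under a drug exposure heading, after a list of every weighing visit, and is paired with use by visit. Protocol 11.3.3 pairs by-visit and overall-period summaries in the same way for compliance. A programmer who pairs dispensing and return weights to obtain use by visit would naturally add them up. The by-visit amount is equally undefined, so it is uneven to read that half of the sentence charitably and the other half literally. And a total of 32 g beside by-visit amounts adding to about 192 g would be conspicuous at table review.

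Much of this stands. A cumulative total is a plausible intention, and the documents do not show what will be programmed. But the phrase gives a start point and an end point for a difference, those two weights come from different containers, and no sum is stated anywhere. The dispensing weights of containers 2 to 6, which the sum needs, appear in the Protocol and not in SAP 13.2.

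Three stronger readings are tempting, and the documents do not support them:

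- *That the study will report exposure at one sixth of its true value.* This follows only from the literal reading, on nominal days with equal starting weights.
- *That Protocol 11.3.4 requires an overall total which the SAP fails to deliver.* It asks only for the amount by weight, which by-visit amounts could satisfy.
- *That compliance, pharmacokinetic or safety results are put at risk.* The diary separately records applications made and missed. SAP 12.3.2 brings in compliance data to support the pharmacokinetic analysis but states no calculation from total weight. No weight-based compliance threshold is defined.

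**Conclusion.** The point holds as a defect of wording with small reach. Followed literally, the overall measure in SAP 13.2 gives about one container's use: about 32 g in the nominal case, where about 192 to 194 g was used. These figures assume full adherence, nominal fill and actuation volume, and visits on nominal days; the 32 g also assumes equal starting weights. The 6 g difference in starting weight is an extreme case taken from an approximate range.

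One descriptive line is affected. The total is recoverable from the by-visit amounts, provided these are computed within container, as the weighings in Protocol 7.1 to 7.3 allow. SAP Appendix A, which is marked preliminary, names no exposure summary table, only the accountability and exposure listings (16.2.5.1 and 16.2.5.2). The correction is low priority and worth making because it costs almost nothing.

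**What to change.** Keep the by-visit summary. In SAP 13.2, replace the phrase on the overall difference with: *total amount used = sum over all dispensed containers of (primed weight with cap at dispensing minus weight with cap at return)*.

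No new rule is needed for incomplete weights. If a container's dispensing or return weight is missing, the total stays missing, consistent with SAP 12.6, which does not impute such data.

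The cost is one phrase in the SAP. Every weight needed is already collected under Protocol 7.1 to 7.3, so no new procedure or data are required.
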